### **Suspected Unexpected Adverse Drug Reaction**

A suspected unexpected ADR is any ADR, the nature or severity of which is not consistent with the applicable product information, e.g., Investigator's Brochure for an unapproved medicinal (investigational) product.

A suspected adverse reaction implies a lesser degree of certainty about causality than an adverse reaction.

### **9.3.3. Serious Adverse Event**

A SAE is any AE that in the view of either the Investigator or Sponsor, meets any of the following criteria:

- Results in death
- Is life threatening: that is, poses an immediate risk of death at the time of the event
- An AE or suspected AE is considered "life-threatening" if, in the view of either the Investigator or Sponsor, its occurrence places the subject at immediate risk of death. It does not include an AE or suspected adverse reaction that, had it occurred in a more severe form, might have caused death
- Requires inpatient hospitalization or prolongation of existing hospitalization
- Hospitalization is defined as an admission of greater than 24 hours to a medical facility and does not always qualify as an AE
- Results in a persistent or significant incapacity or substantial disruption of the ability to conduct normal life functions
- Results in a congenital anomaly or birth defect in the offspring of the subject (whether the subject is male or female)
- Important medical events that may not result in death, are not life-threatening, or do not require hospitalization may also be considered serious when, based upon appropriate medical judgment, they may jeopardize the subject and may require medical or surgical intervention to prevent one of the outcomes listed in this definition. Examples of such medical events include allergic bronchospasm requiring intensive treatment in an emergency room or at home, blood dyscrasias or convulsions that do not result in inpatient hospitalization, or the development of drug dependency or drug abuse

The terms "severe" and "serious" are not synonymous. Severity refers to the intensity of an AE (e.g., rated as mild, moderate, or severe, or according to National Cancer Institute Common Terminology Criteria for AEs [NCI CTCAE]); the event itself may be of relatively minor medical significance (such as severe headache without any further findings).

Severity and seriousness need to be independently assessed for each AE recorded on the eCRF.

#### **9.3.4. AE of Special Interest (AESI)**

For the purpose of this study, severe reductions in platelet count  $< 50,000/\text{mm}^3$  accompanied by a MB event or CRNMB event, or platelet count of  $< 25,000/\text{mm}^3$  independent of a MB or CRNMB event are considered as AEs of special interest and should be subject to 15-day expedited reporting by the Sponsor to the regulatory agencies.

### **9.4. Monitoring and Recording AEs**

Any pre-existing conditions or signs and/or symptoms present in a subject prior to the start of the study (i.e., before informed consent) should be recorded as Medical History and not recorded as AEs unless the pre-existing condition worsened. The Investigator should always group signs and symptoms into a single term that constitutes a **single unifying diagnosis** if possible. Before a diagnosis is confirmed, all symptoms should be reported as separate AEs.

#### **9.4.1. Serious AEs**

In the interest of subject safety, and in order to fulfill regulatory requirements, all SAEs (regardless of their relationship to Study Drug) should be reported to the Sponsor or designee within 24 hours of the Study Center's first knowledge of the event. The collection of SAEs will begin after the subject signs the informed consent form and stop at the end of the subject's Post-Treatment Period which is defined as Study Day 141/ Study Week 21. When the Investigator is reporting by telephone, it is important to speak to someone in person vs. leaving a message. SAEs should be reported using a paper SAE submission form. An Initial Serious AE Form should be completed, and a copy should be faxed or emailed to the Sponsor or designee. The SAE reporting instruction, including the fax number and email address can be found in the Study Reference Manual for the study.

Detailed information should be actively sought and included on Follow-Up Serious AE Forms as soon as additional information becomes available. All SAEs will be followed until resolution. SAEs that remain ongoing past the subject's last protocol-specified Follow-Up visit will be evaluated by the Investigator and Sponsor. If the Investigator and Sponsor agree the subject's condition is unlikely to resolve, the Investigator and Sponsor will determine the follow-up requirement.

#### **9.4.2. Non-Serious AEs**

The recording of non-serious AEs will begin after the subject signs the informed consent form and will stop at the end of the subject's Post-Treatment Period, which is defined as Study Day 141/ Study Week 21. The Investigator will monitor each subject closely and record all observed or volunteered AEs on the AE Case Report Form.

#### **9.4.3. Evaluation of AEs (Serious and Non-Serious)**

The Investigator's opinion of the following should be documented on the AE Case Report Form:

##### **9.4.3.1. Relationship to the Study Drug**

The event's relationship to the Study Drug (ISIS 757456 or placebo) is characterized by 1 of the following:

- **Related:** There is clear evidence that the event is related to the use of Study Drug, e.g., confirmation by positive re-challenge test
- **Possible:** The event cannot be explained by the subject's medical condition, concomitant therapy, or other causes, and there is a plausible temporal relationship between the event and Study Drug (ISIS 757456 or placebo) administration
- **Unlikely/Remote:** An event for which an alternative explanation is more likely (e.g., concomitant medications or ongoing medical conditions) or the temporal relationship to Study Drug (ISIS 757456 or placebo) administration and/or exposure suggests that a causal relationship is unlikely (for reporting purposes, Unlikely/Remote will be grouped together with Not Related)
- **Not Related:** The event can be readily explained by the subject's underlying medical condition, concomitant therapy, or other causes, and therefore, the Investigator believes no relationship exists between the event and Study Drug

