### 5.1. Inclusion Criteria

1. Must have given written informed consent (signed and dated) and any authorizations required by local law and be able to comply with all study requirements
2. Males or females aged 18–75 inclusive and weighing  $\geq 50$  kg at the time of informed consent
3. Satisfy the following:
  - a. Females: must be non-pregnant and non-lactating, and either:
    - i. surgically sterile (e.g., tubal occlusion, hysterectomy, bilateral salpingectomy, bilateral oophorectomy) or,
    - ii. post-menopausal (defined as 12 months of spontaneous amenorrhea in females  $> 55$  years of age or, in females  $\leq 55$  years, 12 months of spontaneous amenorrhea without an alternative medical cause and follicle stimulating hormone (FSH) levels in the postmenopausal range for the laboratory involved)
  - b. Males: Surgically sterile (i.e., bilateral orchidectomy) or abstinent\*, if engaged in sexual relations with a woman of child-bearing potential (WOCBP), the subject or subject's non-pregnant female partner must be using a highly effective contraceptive method from the time of signing the informed consent form until at least 13 weeks after the last dose of Study Drug (ISIS 757456 or placebo)

\* True abstinence (i.e., refraining from heterosexual intercourse throughout the duration of study participation) is only acceptable. Periodic abstinence (e.g., calendar, ovulation, symptothermal, post-ovulation methods), declaration of abstinence for the duration of a trial and withdrawal are not acceptable methods of contraception

4.  $BMI \leq 35.0 \text{ kg/m}^2$
5. Brachial circumference  $\geq 22$  and  $\leq 37$  cm (8.7 and 14.6 inches)
6. Subject must have been diagnosed with essential HTN for a minimum of 3 months prior to screening
7. At Screening, the subject must have a plasma AGT concentration  $\geq 20 \text{ } \mu\text{g/mL}$ . Up to 1 additional repeat test may be allowed in order to qualify with consultation of the Sponsor Medical Monitor
8. At Screening, the subject must have been on a stable regimen of 2 to 3 antihypertensive medications for at least 1 month prior to screening and will be required to maintain this regimen throughout the Study, using either an angiotensin-converting enzyme inhibitor (ACEi) or an angiotensin II receptor blocker (ARB), as well as 1 or 2 additional antihypertensive medications in the following categories:
  - a. beta blocker
    - i. acebutolol
    - ii. atenolol
    - iii. betaxolol
    - iv. bisoprolol

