#### **9.3.2. Adverse Drug Reaction and Suspected Unexpected Adverse Drug Reaction**

##### **Adverse Drug Reaction (ADR)**

In the *pre-approval* clinical experience with a new medicinal product or its new usages, particularly as the therapeutic dose(s) may not have been established, ADR is defined as follows:

All noxious and unintended responses to a medicinal product related to any dose should be considered ADRs.

The phrase "responses to a medicinal product" means that a causal relationship between the medicinal product and the AE has been determined by the Sponsor as at least a reasonable possibility, i.e., the relationship cannot be ruled out.

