#### 9.4.3.6. Follow-up of Adverse Event

##### Investigator Follow-Up

During the Study Period, the Investigator should follow each AE until the event has resolved to baseline grade or better, the event is assessed as stable, the subject is lost to follow-up, or the subject withdraws consent. Every effort should be made to follow all SAEs considered to be related to Study Drug or related to study procedures until a final outcome can be reported.

Resolution of AE (with dates) should be documented on the AE eCRF and in the subject's medical record to facilitate source data verification.

Investigator should follow-up or support the Sponsor's effort to follow up with all pregnancies reported during the study from either the study subject or the female partner of male study subject until pregnancy outcome is available.

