### 3.7.2 Adverse Events

The incidence of adverse events (AEs) will be summarized by Medical Dictionary for Regulatory Activities (MedDRA) version 22.0 (or higher) preferred term and system organ class for:

- Any treatment emergent adverse events (TEAEs).
- Related TEAEs. Related is defined as "Related", "Possible", or missing relationship to study drug.
- Any TEAEs by severity. At each severity level of subject summarization, a subject is classified according to the highest severity if the subject reported one or more events. AEs with missing severity will be categorized as "Missing" for this summary.
- Serious TEAEs (Treatment-emergent SAEs).
- TEAEs leading to permanent study drug discontinuation.

Serious and non-serious AEs that lead to study discontinuation or investigational drug discontinuation will be listed separately. Non-treatment emergent adverse event will be included and be noted in the subject AE listing.

To determine the AE as treatment-emergent or not, if there is no "Formlink" link, and the AE (start date/time) occurs after the subject's first dosing date/time, then the AE is treatment-emergent. Otherwise, if the AE (start date/time) occurs prior to the subject's first dosing date/time, then the AE is not treatment-emergent.

In addition, if there is a "Formlink" link between two AE records, then we compare them pairwise, and consider two cases, where we compare the AE severity (mild/moderate/severe) and seriousness (Yes/No) between the two records in the pair. We chronologically order the 2 records (by AE start date) and refer to the "first" and "second" AE.

Case 1: The first AE record in the pair occurs before first dosing, and the second AE record occurs after first dosing.

If the AE severity or seriousness of the second record is worse than that of the first record, then only the second AE is deemed as a TEAE. Otherwise, neither record is considered as TEAE.

Case 2: Both AE records in the pair occur after first dosing.

If the AE severity or seriousness of the second record is worse than that of the first record, then two TEAEs are recorded. Otherwise only the first AE record is deemed as a TEAE.

All TEAEs identified based on the rules above will be summarized in the event number analysis.

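### The *Possible* level of the causality scale is stricter than the protocol's own adverse drug reaction standard and has no place for two-cause events, so the related-TEAE summaries are likely to undercount them or classify them inconsistently

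*Combined protocol and SAP*

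**What the plan says.** Protocol 9.4.3.1 gives four levels of relationship to Study Drug, recorded as the Investigator's opinion (9.4.3):

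- *Related*: needs clear evidence for Study Drug, with a positive re-challenge given as the example.
- *Possible*: "The event cannot be explained by the subject's medical condition, concomitant therapy, or other causes", and in addition the timing is plausible.
- *Unlikely/Remote*: an alternative explanation is more likely, or the timing makes a causal link unlikely. The section adds that "for reporting purposes, Unlikely/Remote will be grouped together with Not Related".
- *Not Related*: the condition, concomitant therapy or another cause readily explains the event, and the Investigator therefore believes there is no relationship.

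SAP 3.7.2 builds its table from this scale: "Related is defined as 'Related', 'Possible', or missing relationship to study drug". Protocol 10.6.2 promises summaries of TEAEs, and of serious TEAEs, potentially related to Study Drug.

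For an adverse drug reaction, Protocol 9.3.2 asks for a causal relationship that "has been determined by the Sponsor as at least a reasonable possibility, i.e., the relationship cannot be ruled out".

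Inclusion criterion 8 (Protocol 5.1) has every subject "using either an angiotensin-converting enzyme inhibitor (ACEi) or an angiotensin II receptor blocker (ARB), as well as 1 or 2 additional antihypertensive medications".

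**The concern.** The trial adds a drug acting on the renin-angiotensin-aldosterone system (RAAS) to a regimen that already contains one. Protocol 2.2 says that combining agents in this pathway has been complicated by hyperkalemia, hypotension and acute renal failure. When one of these occurs on treatment, the natural assessment will often be that Study Drug, the background drug or the two together could be responsible. A causality scale for this trial needs a level for that judgement.

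At stake are the related-TEAE summaries, which readers commonly use to see what investigators suspected of the drug. If two-cause events are pushed into the unrelated group, or go in or out according to how each site reads the definition, those summaries understate suspicion about the mechanism-based risks of most interest here.

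**Working it through.** The plan states no figure on this point. The check sets the definitions against one test case and then traces where the result goes.

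**Test case.** An event with plausible timing after dosing, for which the Investigator considers Study Drug and the background ACE inhibitor or ARB equally credible causes, without clear evidence for either.

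| Level (9.4.3.1) | What it needs | Test case | Counted as related (SAP 3.7.2) |
|---|---|---|---|
| *Related* | Clear evidence for Study Drug | Fails: no clear evidence | Yes |
| *Possible* | No other explanation, and plausible timing | Fails the first condition | Yes |
| *Unlikely/Remote* | Alternative more likely, or timing against | Fails both: alternatives equal, timing plausible | No |
| *Not Related* | Readily explained otherwise, and the Investigator believes there is no relationship | Fails: that belief is not held | No |
| Missing | No assessment recorded | Does not apply | Yes |

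The test case meets no level. Under 9.3.2 it would qualify, because the relationship cannot be ruled out. The SAP rule also has an odd result: an event left unassessed counts as related, while one assessed as equally attributable to Study Drug may not.

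**Does the case arise here?** Background ACE inhibitor or ARB use is universal by inclusion criterion 8. Protocol 8.6.4 itself names these drugs among medications affecting potassium, and 8.6.5 refers to other antihypertensives that could affect blood pressure. The protocol therefore treats background therapy as a credible contributor.

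**Can clear evidence rescue the event?** Sometimes. Dosing may resume after a potassium hold (8.5.4) or a hypotension pause (8.5.5), which could give re-challenge information. Events that meet the renal, potassium or low-blood-pressure stopping rules (8.6.2, 8.6.4, 8.6.5) end dosing permanently, so no re-challenge follows. Under 8.6.4 and 8.6.5 background drugs may be stopped along with Study Drug, so recovery would not separate the two.

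**Which outputs depend on the scale?**

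- Dependent: the related-TEAE table in SAP 3.7.2, and the two potentially-related summaries in Protocol 10.6.2. The summary of related serious events is listed only in the protocol.
- Not dependent: all TEAEs, TEAEs by severity, serious TEAEs and TEAEs leading to discontinuation (SAP 3.7.2), and the safety endpoint, which is all TEAEs including hypotension (SAP 1.3.3).

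**Scale of one reclassification.** About 30 subjects randomized 2:1 gives 30 × 2/3 = 20 active and 30 × 1/3 = 10 placebo. One subject moved into or out of the related group changes the active percentage by 1/20 = 5 points, or the placebo percentage by 1/10 = 10 points.

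**The case against.** A reader might infer that hypotension, hyperkalemia and renal events are barred from the related table by definition, and that it will be close to empty for them. The documents do not support that, for four reasons.

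1. *Related* has no clause about concomitant therapy, re-challenge is only its example, and a missing relationship also counts.
2. An available explanation need not be the explanation. Subjects have been on an unchanged regimen for at least one month before screening (8.2), still have SBP above 140 mmHg before the first dose (5.1), and are excluded if screening potassium exceeds 4.9 mmol/L (5.2). An Investigator may fairly judge that this regimen does not explain a new event.
3. Protocol 2.2 ties these complications to using two or more agents in the pathway. Criterion 8 allows an ACE inhibitor or an ARB, and 5.2 excludes renin inhibitors, so the multi-agent risk begins when Study Drug is added.
4. Protocol 8.10.1 limits concomitant therapy to drugs that are not protocol-specified, whereas the background antihypertensives are listed in 8.2 as protocol-required. They arguably fall outside the clause.

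All four stand against the stronger reading. They do not remove the gap. Other causes, which the *Possible* definition also lists, can still cover the background drugs. The second and third points show that sites can reasonably differ, which is itself the inconsistency.

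A reader might also infer harm to follow-up or expedited reporting, since 9.4.3.6 says "Every effort should be made to follow all SAEs considered to be related to Study Drug". But 9.4.1 already has all SAEs reported regardless of relationship and followed until resolution, and 9.2 gives the Sponsor its own reasonable-possibility judgement for SUSARs. Finally, 9.3.2 concerns the Sponsor's determination and 9.4.3.1 the Investigator's, so the two are different standards rather than a direct contradiction.

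**Conclusion.** The point holds as a defect of wording with limited reach. *Possible* is stricter than the standard in 9.3.2, and the scale has no level for a well-timed event with two equally credible causes. In a trial where all subjects take a RAAS blocker, such events are foreseeable, and the related-TEAE summaries are likely to undercount them or classify them inconsistently. This assumes that at least some investigators apply the definition as written.

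The size of the undercount cannot be derived from the documents, which give no expected rate of these events and no indication of how sites will read the definition. The effect is confined to the relatedness summaries and applies in both blinded arms. The comparison of all TEAEs with placebo is untouched. It is worth correcting because the summaries are promised outputs and the correction is cheap.

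**What to change.** - In Protocol 9.4.3.1, redefine *Possible* as an event with a plausible temporal relationship to Study Drug whose relationship cannot be ruled out, even if the medical condition or other therapy, including the background antihypertensives, could also explain it.
- Keep *Unlikely/Remote* for events where the alternative is more likely.
- State in the CRF completion guidance how background antihypertensives are treated in causality assessment, since 8.10.1 and 8.2 leave open whether they are concomitant therapy.

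SAP 3.7.2 needs no change, because its definition of related picks up the revised level. The cost is one protocol sentence and a line of CRF guidance. The downside is somewhat higher related-TEAE counts in both arms.

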#### 9.4.3.2. Severity

The severity of AEs and SAEs relating to laboratory tests and AEs at the injection site will be graded based on criteria from the Common Terminology Criteria for AEs (CTCAE) Version 5.0, November 2017 (refer to [Appendix D](#)). Any AE not listed in Appendix D will be graded as follows:

- **Mild:** The event is easily tolerated by the subject and does not affect the subject's usual daily activities
- **Moderate:** The event causes the subject more discomfort and interrupts the subject's usual daily activities
- **Severe:** The event is incapacitating and causes considerable interference with the subject's usual daily activities

If the event is an SAE, then all applicable seriousness criteria must be indicated (criteria listed in Section [9.3.3](#)).

#### 9.4.3.3. Action Taken with Study Drug

Action taken with Study Drug (ISIS 757456 or placebo) due to the event is characterized by 1 of the following.

- **None:** No changes were made to Study Drug (ISIS 757456 or placebo) administration and dose
- **Not Applicable:** SAE/AE was reported during the Screening Period prior to Study Drug administration or during the Post-Treatment Period
- **Permanently Discontinued:** Study Drug was discontinued and not restarted
- **Temporarily Interrupted, Restarted – Same Dose:** Dosing and/or dosing frequency was temporarily interrupted/changed or delayed due to the AE and restarted at the same dose

- **Reduced Dose:** Dosing was reduced, temporarily interrupted or delayed due to the AE and restarted at the next lower dose or reduced dosing frequency

#### 9.4.3.4. Treatment Given for AE

Any treatment (e.g., medications or procedures) given for the AE should be recorded on the AE Case Report Form. Treatment should also be recorded on the concomitant treatment or ancillary procedures eCRF, as appropriate.

#### 9.4.3.5. Outcome of the AE

If the event is a non-serious AE, then the event's outcome is characterized by 1 of the following:

- **AE Persists:** Subject terminates from the trial and the AE continues
- **Recovered:** Subject recovered completely from the AE
- **Became Serious:** The event became serious (the date that the event became serious should be recorded as the Resolution Date of that AE and the Onset Date of the corresponding SAE)
- **Change in Severity (if applicable):** AE severity changed

If the event is an SAE, then the event's outcome is characterized by 1 of the following:

- **Ongoing:** SAE continuing
- **Persists (as non-serious AE):** Subject has not fully recovered but the event no longer meets serious criteria and should be captured as an AE on the non-serious AE eCRF (the SAE resolution date should be entered as the date of onset of that AE)
- **Recovered:** Subject recovered completely from the SAE (the date of recovery should be entered as the SAE resolution date)
- **Recovered with Sequelae:** The signs/symptoms of the reported SAE have improved but not completely resolved, and a new baseline for the subject is established since full recovery is not expected
- **Fatal:** Subject died (the date of death should be entered as the SAE resolution date)
- **Unknown:** The outcome of the reported SAE is not available, e.g., subject is lost to follow-up

